Centers also need to keep a listing of why the participant who was told about the study decided not to participate. These reasons are recorded on "The Reasons Why Participants who are Approached and do not Consent" tally sheet. This evaluation of reasons for non-enrollment and chart-based outcomes of non-enrollees is key to planning for dissemination of this technique within diverse VA sites and populations.

Criteria for exclusion will include:

- Active prescriptions for > 1 antihypertensive agent (excluding chronic agents prescribed primarily for other purposes, such as alpha blockers for prostate disease or PTSD);
- Known allergies to 2 or more antihypertensive agents;
- Specific reasons for a blood pressure target different from in-clinic target of 130/80, or a corresponding home management goal of 120/80
- Currently not primarily in charge of his/her own medication administration (e.g. those living in institutions or with dementia or other limitations making self-medication care not possible);
- Life expectancy of < 12 months;
- Blood pressure at screening visit > 180 mm Hg systolic or > 110 diastolic, or < 130 systolic; screening cognitive function (Montreal Assessment of Cognitive Function, MoCA)⁵⁰ score less than 25;
- eGFR < 25 ml/min /1.73m² or end-stage renal disease (ESRD);
- Inability to use a standard home blood pressure cuff;
- Known secondary cause of hypertension that causes concern regarding safety of the protocol, in the opinion of the site investigator;
- Cardiovascular event or hospitalization for unstable angina within last 3 months;

- Symptomatic heart failure within the past 6 months or left ventricular ejection fraction < 35%;
- Pregnancy or planned pregnancy, or of child-bearing age not using birth control;
- Current participation in another clinical trial;
- Major factors judged to be likely to significantly limit comprehension of or adherence to interventions including dementia, psychiatric disease, or substance abuse.
- Cancer treatment within the last year

Primary care physicians and study staff will be able to exclude participants based on their judgment of the patient's capability to undergo the intervention.

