During the screening or baseline study visit, all participants will receive training to appropriately check blood pressure at home using study-issued home blood pressure monitors. A baseline chemistry panel and assessment of albuminuria will be ordered, if not completed clinically within 3 months of the study visit.

Both groups will complete an initial study visit with the study team and physician and complete a 24-hour ABPM session. The ABPM session can be done prior to training for the intervention participants.

4. Random allocation and blinding. Randomization will be 1:1 intervention/control. Randomization will be done by a central system, stratified by degree of hypertension at initial visit (> 160 systolic or below) and block-randomized by clinical sites using the centralized randomization tool through the Health Services Research Center data servers. The study participants and personnel will be unblinded. The research assistant in charge of checking blood pressures at the initial, 6-month, and 12-month visits may be aware of treatment allocation but will use standard procedures and an automated Omron cuff, using the SPRINT study blood pressure measurement protocol (5 minutes of quiet rest followed by 3 automated blood pressures at one-minute intervals, averaging last 2 to determine in-clinic BP), to ascertain blood pressures to avoid digit preference and bias.

5. Follow-up study visits: Participants in both randomization arms will then return for 6-month and 12-month study visits at which times blood pressure will be checked by a research assistant, and participants will complete questionnaires similar to those obtained at baseline, blood and urine studies for kidney function and albuminuria (as part of routine clinical care) at 12-month visit, and repeat ABPM at both 6 and 12-month visits.

6. Usual care and intervention protocols. Both groups will be issued a home blood pressure cuff with data recording capabilities identical to that in the active arm of the study, (Microlife BP, Microlife USA Inc), will meet the study physician and have questions answered, and will be instructed to record and share results with their primary care physician at routine clinic visits. The patient's and provider's willingness to titrate to a clinical goal of 130/80 (home goal of 120/75) will be confirmed.

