4.2 Visit Procedures

Screening Visit procedure

- 1. Verify participant's interest in study.
- 2. Obtain in person study consent and HIPAA authorization for main trial prior to randomization (randomization can also occur at time of screening visit if time allows)
- 3. Continue collection of screening information, including such items as contact information, additional eligibility information including BP measurement, concomitant medications, medical history, and MoCA. If time allows, questionnaires can be completed once at Screening or Baseline visit.

Baseline visit (Randomization Visit)

- 1. Reconfirmation that all inclusion/exclusion criteria were addressed at screening
- 2. Verification of participant consent and HIPAA authorization.
- 3. Verification of participant contact information
- 4. Completion of the study randomization procedure and baseline data collection
- Issuance of home BP cuff (to all participants) and initial training session (for active selfmanagement). Issuance of home BP cuff can also be done at Screening visit, if time allows.

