2. Data analytic plan. Preliminary analyses will begin with an examination of the distribution of variables to assess their characteristics (means, standard deviations, medians, outliers), to provide descriptive statistics of the study population, and to allow assessment of randomization. Continuous measures will be tested for normality and non-normally distributed variables will be transformed to meet the normal distribution assumption for linear models. Randomization will be tested by performing a series of Wilcoxon rank sum test and Fisher's exact test to compare the two study groups on demographic and initial clinical variables. Randomization will be stratified by BP level at entry (at 160 systolic), and block (of 10) randomization will be done for each clinical site. We will pursue standard intention-to-treat analysis of the randomized group as a primary analysis, with the ANCOVA analyses as secondary approaches should randomization have failed on critical metrics. Blinded randomization should assure that the distribution of risk factors will not confound the associations of interest, however inclusion as covariates may reduce error variance and may therefore improve statistical power. In case of missing data, appropriate data analytic techniques will be used, which may include deletion, imputation, inclusion of an indicator of missing values, or pattern-mixture modeling. All analyses for the primary aims will use an intention-to-treat approach. Sensitivity analyses will consider the importance of missing data or loss-to-follow-up (last observation carried forward, vs. imputation of data from other sources such as clinic visits). Outcomes will be analyzed using open source statistical software R.65

For ambulatory blood pressure data, each individual 24-hour BP reading will be assessed for adequacy (defined as at least 14 daytime and 7 nighttime readings) and transformed into summary variables (e.g. 24-hour mean blood pressures). Home blood pressure data will be recorded in 2 ways: (1) the internal memory of the home BP device will be downloaded directly at the time of 6- and 12-month visits and (2) in the event of a memory failure, the participants' log book records will be reviewed and values entered. Questionnaire data will be entered and encoded along appropriate scales and scores on these questionnaires will be examined in univariate analyses to determine response distributions and coding.

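### A single fixed block size of 10, printed in the protocol of an open trial, would let staff who keep a tally deduce about one allocation in six, and varying the block size is a cheap remedy.

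*Combined protocol and SAP*

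**What the plan says.** Chapter 2, section 4 (Random allocation and blinding) sets the ratio: "Randomization will be 1:1 intervention/control". Allocation is "stratified by degree of hypertension at initial visit (> 160 systolic or below) and block-randomized by clinical sites using the centralized randomization tool". The same section says "The study participants and personnel will be unblinded".

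Chapter 9, section 2 (Data analytic plan) gives the block size: "block (of 10) randomization will be done for each clinical site". It mentions no variation in size and does not say that the size is withheld from recruiting staff. The same section relies on concealment: "Blinded randomization should assure that the distribution of risk factors will not confound the associations of interest".

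After the exclusion list in Chapter 2, section 2, the plan adds that "Primary care physicians and study staff will be able to exclude participants based on their judgment" of whether the patient can carry out the intervention. Section 4.2 (Visit Procedures) lists "Reconfirmation that all inclusion/exclusion criteria were addressed at screening" as the first step of the baseline visit, ahead of the randomization step. It also allows randomization at the screening visit if there is time.

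**The concern.** In an open trial the people who recruit can see past allocations. A central tool hides the future list, but it cannot stop anyone from counting. With a known fixed block size, the tail of each block follows from what has already been assigned.

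This matters because a discretionary exclusion is available before randomization, and it concerns fitness for one arm only. A staff member who knew that the next slot was self-management could, even without intent, be stricter with a patient who seemed less able. Selection of that kind makes the arms differ at entry. Intention-to-treat keeps patients in the arm they were assigned but does nothing about who was let in. The primary test in Chapter 9 is an unadjusted t-test on change in systolic pressure.

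**Working it through.** **Inputs from the documents.** One block size of 10 (Chapter 9, section 2). A 1:1 ratio, so 5 + 5 per block (Chapter 2, section 4). About 250 participants in follow-up at San Diego and 150 at San Francisco (Chapter 2, section 1). Total 400 (section F4).

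**Assumptions.** 10–30% of participants are above 160 mm Hg. If each San Diego clinic is blocked separately, the split is 125 at the main clinic and 25 at each of the five listed CBOCs.

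**The plan's own figure.** The plan gives no figure for predictability. Its total of 400 serves here only as the count, and it checks out: 2 × (1.96 + 0.84)² × 16² / 5² gives 161 per arm, and 161 / 0.80 gives 202, against the stated 200. Power with 160 completers per arm is 79.8%.

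**Step 1: certain allocations in a complete block.** There are C(10,5) = 252 possible blocks. The allocation at position k is certain when one arm has used its five places in the first k − 1. The probability is 2 × C(k − 1, 5) / 252.

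| Position | Calculation | Certain |
|---|---|---|
| 6 | 2 × 1 / 252 | 0.8% |
| 7 | 2 × 6 / 252 | 4.8% |
| 8 | 2 × 21 / 252 | 16.7% |
| 9 | 2 × 56 / 252 | 44.4% |
| 10 | 2 × 126 / 252 | 100% |

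The sum is 420 / 252 = 1.667 per block. This agrees with the closed form 2m/(m + 1) with m = 5. The share is 1.667 / 10 = 16.7%, and 400 × 1/6 is about 67.

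**Step 2: unfinished blocks and the definition of a site.**
- Blocks by site only: 25 + 15 = 40 complete blocks, and 40 × 1.667 / 400 = 16.7%.
- Two sites by two SBP strata: 15.8–16.7%. For example, with 10% above 160 the cells are 25, 225, 15 and 135. They hold 38 complete blocks, and 38 × 1.667 / 400 = 15.8%.
- Each CBOC blocked separately, by SBP stratum: 12.9–15.4%.

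**Step 3: best guess over all positions.** If the observer always guesses the arm with more places left, the expected number correct per block is m + 2^(2m − 1)/C(2m, m) − 1/2 = 5 + 512/252 − 0.5 = 6.53. That is 65.3%, against 50% with no information.

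**Step 4: varied sizes.** Simulations used an observer who knows the set of sizes and updates after each allocation.

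| Scheme | Certain | Best guess |
|---|---|---|
| Fixed 4 | 33.3% | 70.8% |
| Fixed 10 | 16.7% | 65.3% |
| Random 4/6/8 | 2.1% | 68.2% |
| Random 6/8/10 | 1.7% | 66.4% |
| Random 8/10/12 | 1.1–1.4% (separate runs) | about 65% |

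With 8/10/12, allocations predictable with more than 90% confidence are about 3%.

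**Step 5: what this means for bias.** Let staff shift the prognosis of those enrolled by +d or −d according to the arm they expect; d is unknown.
- If they act on every best guess, the difference between arms is 2d(2p − 1), where p is best-guess success. With p = 0.653 this is 2d × 0.306; with p = 0.649 it is 2d × 0.298, a cut of about 3%.
- If they act only when certain, the difference is 2d × 0.167 with fixed blocks and 2d × 0.011 to 2d × 0.014 with varied sizes. Nearly all of it goes.

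**The case against.** The strongest objection is that the remedy leaves the guessing advantage almost untouched, as the first part of step 5 shows. That stands. The benefit depends on staff being more likely to act on a certain slot than on a probable one, and the fix should be presented in those terms.

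A reader might infer that staff know the allocation before they approach a patient. The documents do not support this. The SBP stratum depends on pressure at the initial visit, section 4.2 puts consent before the screening measurements, and about 30% of consented San Diego subjects are expected to fail screening. At approach, staff cannot be sure of the patient's cell or whether this patient will be the next one randomized in it. Randomizing at the screening visit shortens the window after that, but does not close it.

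A reader might also infer that concealment has been broken. Nothing in the documents shows this. The deduction requires staff who know the block size and follow every allocation in the cell, and the plan does not say who sees cumulative allocations.

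Three further points carry some weight. Most eligibility criteria are objective, and the discretionary one is limited to capability. Patients found incapable after allocation stay in their arm by intention-to-treat, which closes that route. The planned baseline comparisons and conditional ANCOVA would detect or adjust for some imbalance, but only in measured factors; motivation and aptitude for self-management may be poorly captured. Finally, a fixed block of 10 is a legitimate and fairly large choice, and smaller blocks would be worse. That does not count against varying the size around 10.

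**Conclusion.** The point holds as a weakness in allocation concealment. For staff who know the block size and keep a tally, 16.7% of allocations in complete blocks are deducible, or about 13–17% once unfinished blocks and possible separate blocking of CBOCs are allowed for. The lower end rests on assumed cell sizes. The plan does not say outright that blocks are formed within site by SBP stratum, but blocking by site alone gives the same 16.7%.

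The effect on the treatment estimate cannot be sized from the documents, because it depends on whether and how strongly staff would act. The severity is modest. The change is still worth making, because the trial is open, one exclusion is discretionary and tied to one arm, and the analysis section counts on concealment to protect the comparison.

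**What to change.** Have the central randomization tool draw block sizes at random from 8, 10 and 12 within site and SBP stratum. State in the protocol only that blocks of varying size are used, and move the sizes to a document held at the data centre. Say explicitly that blocks are formed within site by SBP stratum, and what counts as a site. The documents do not show whether enrolment has begun; if it has, apply the change to allocations still to be made.

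The fall in certain allocations, from 16.7% to about 1–1.5%, does not depend on secrecy, because the simulated observer knew the set of sizes. Withholding the sizes should help further, but that part has not been quantified.

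The cost is a setting in the existing tool and a wording change. The maximum within-block imbalance rises from 5 to 6. Sample size, visits and endpoints do not change.

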Preferred medications are any VA formulary medication, to include in order of general preference:

- Sustained-release calcium channel blockers (CCBs)
- Thiazide-type diuretics
- Loop diuretics
- Angiotensin converting enzyme (ACE)-inhibitors
- Angiotension receptor blockers (ARBs)
- Beta-blockers
- Direct vasodilators
- Potassium-sparing diuretics
- Alpha1-receptor blockers
- Adrenergic inhibitors

To facilitate titration, combination pills are encouraged.

Chapter 4.c Post Randomization Visit Procedures 6 mos and 12 mos

These visits should be scheduled at the time of the baseline visits. Participants should receive a reminder phone call 1-2 weeks prior to the visit to ensure that the date remains acceptable. Participants should bring all written logs of home blood pressure (both groups) for collection and copying (participants may return with their logs to home if they so desire).

At the 6 and 12 month visits, procedures and surveys should be completed per the table above and blood pressure recorded in the study visit. 24-hour blood pressure monitors will again be used so participants should be reminded ahead of time to plan for this, and reminded at the visit to mail the device back promptly.

At the 12 month visits, participants should be reminded to return the equipment issued for the study. This includes blood pressure cuffs as well as logs and notebooks. They should be seen by the study physician at this visit and reminded that their blood pressure care is fully managed by their primary care physician from this point forward.

Chapter 5. Retention, Adherence

Adherence and retention for a clinical trial are essential. In this trial, we foresee several potential barriers and solutions:

1) Disappointment with being in the 'usual care' arm leading to lack of follow-up for the 6 and 12 month visits

Approach: make sure randomization is not set up as a 'win/lose' situation Remind all participants that the financial incentives are for completion of 6 and 12 month visits

2) Frustration/fear/anxiety about self-monitoring, leading to avoidance of the intervention protocol, repeated phone calls to study staff or PCP, etc

Approach: up-front support and extra training visits as needed; but need to avoid 'taking over' from primary care and over-supporting during period of test of self-monitoring. If participant calls frequently remind them about 6 and 12 month visits and alert their PCP, or alert study physician to contact PCP

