At the baseline, six-month, and twelve-month visits, the blood pressure will be measured by a research protocol (3 measurements with interval pauses as above). The blood pressure from the research study visit on the day of randomization will serve as the baseline study visit for this trial. The outcome blood pressure will be the similarly measured (research protocol) blood pressure at the 12 month study visit.

ABPM set-up will be done according to our previously used Spacelabs protocols from SPRINT study.

All study instruments will be administered by research staff in-person with patients at the baseline, 6 and 12 month visits.

Chapter 8. Safety Monitoring and Reporting

The main clinical adverse events that will be monitored during this trial are those related to overor under-treatment of blood pressure. These were not different from usual care during the two studies of similar interventions in the UK, and only 3% of those in the intervention group deviated from self-titration protocols in those studies. Nevertheless, we plan to actively monitor for these issues by scheduled chart review for clinical or ER visits, hospitalizations, and potentially study-related serious adverse events (e.g. syncope, hypertensive urgency, stroke, MI, death). Other adverse events potentially related to the study will also be collected (e.g. medication side effects, abnormal laboratory findings including sodium < 130 or potassium <3 (for those on thiazide); potassium >6 for those on ACE; creatinine 50% higher than baseline).

We have assembled a DSMB for this study given the potential risks of self-management of blood pressure. This will consist of experienced nephrologist-epidemiologists and a general internist, all working in the VA system. Assisted by the study statistician they will review AEs and BP data in both groups at the point where each group of 100 participants have reached the six-month time point.

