Hypothesis 1a (primary hypothesis): Improvement in systolic blood pressure measured at clinic from baseline to 12 month will be greater in the intervention vs. the usual care group. The primary outcome is the absolute change of systolic blood pressure (SBP) measured in mmHg from the study clinic randomization visit to the month 12 visit. The primary statistical test for comparison for continuous outcomes is a simple t-test across the two randomized groups. As a secondary analysis, in case of issues with randomization for differences in baseline BP, an Analysis of Covariance (ANCOVA) model with intervention group as a main effect and baseline SBP as a covariate will be fitted to study the group difference in change of SBP from baseline to week 12. Baseline sociodemographic and other clinically important characteristics at baseline will be assessed for imbalance between the two study groups and their association with the outcome using a univariate analysis (Wilcoxon rank-sum test, Kruskal-

Wallis test, Spearman correlation coefficient or Fisher's exact test). These variables will be included as covariates in the ANCOVA model if found to be moderately associated (p < 0.15) with the outcome or unbalanced (p < 0.10) between groups. Purposeful model selection method⁶⁶ will be used to select the main effects in the final model, all covariates that are significant at p < 0.10 will be kept in the final model. To assess the difference in the effect of patient characteristics on the outcome between intervention and control group, we will study the interaction between treatment and patient characteristics in the final model, as appropriate. Prespecified interactions will include analyses of effects in, older vs. younger participants (< 65), , African-American vs. other races, and initial BP level (> 160 vs. lower), and educational level (less than high school degree or more). We recognize the possibility of chance findings due to multiple comparisons by these strata, P-values for interaction will be evaluated conservatively, and data will be conservatively interpreted. If numbers in any of these subgroups are too small to allow a reasonable investigation, the subgroup analysis will be dropped. Forest plots will be constructed to assess whether subgroup effects are similar, in exploratory analyses.

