F4. Sample size and power. Power analyses were conducted for detecting the difference in mean change of SBP over 12 months between the subjects with intervention and subjects in control group (Hypothesis 1a) assuming a two-sided Type I error of 0.05 and an attrition rate of 20% at month 12, with sample size estimation based on a 2 sample t-test. Based on prior literature in hypertension, we assumed a standard deviation of individual change in BP over 1 year of 16 mm Hg (conservative estimate based on standard deviation of blood pressure measurement in multiple clinical studies,^{40,41} and similar to that seen in our pilot data in older CKD patients⁴³) and considered a difference of 5 mm Hg to be a clinically significant difference, a smaller difference than was seen in the TASMIN studies (which found differences of 5.4 and 9.2 mm Hg with similar sample sizes). With a 20% attrition rate, we need to recruit 200 participants per arm, or 400 total participants (total of 320 participants completing the study) to have 80% power to detect a minimum of 5mmHg (Cohen's effect size of 0.31) for the difference in mean change of SBP over 12 months between intervention and control groups. Data Safety Monitoring. We will, in addition to proactively collecting adverse events, hospitalizations, clinic visits and protocol violations, collect blood pressure data from participants at the six-month in-person visit as they self-monitor during the study. At the point where 100, 200, and 300 participants cross the 6-month point, the DSMB will review the accumulated information both from the in-clinic blood pressure averages as well as the log reports from the home BP cuffs in both groups. Although TASMIN investigators reported a less than 3% rate of protocol violations in the self-management participants, we are interested in tracking this in our intervention arm as well at the midpoint of the study. Inappropriate requests for study prescriptions will be tabulated. DSMB members will be able to examine whether out-of-range readings led to appropriate participant behavior. If this rate is considered to be too high by the DSMB, they will have the option of halting the study due to safety concerns. They will also have the option of halting the study due to SAEs or other concerns.

Chapter 10. Data Security and database management

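### With 20% attrition planned, the primary 12-month t-test needs a named missing-data method that uses the 6-month research SBP, and LOCF should not be the main check

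*Combined protocol and SAP*

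**What the plan says.** Chapter 9, Hypothesis 1a, defines the outcome as the SBP change from the randomization visit to month 12 and states: "The primary statistical test for comparison for continuous outcomes is a simple t-test across the two randomized groups". Section F4 sets the sample size "assuming a two-sided Type I error of 0.05 and an attrition rate of 20% at month 12", giving 400 randomized and a "total of 320 participants completing the study".

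On missing data, the data analytic plan in Chapter 9 promises appropriate techniques, "which may include deletion, imputation, inclusion of an indicator of missing values, or pattern-mixture modeling". It labels the primary-aim analyses intention-to-treat and names two sensitivity approaches: "last observation carried forward, vs. imputation of data from other sources such as clinic visits". It states no missingness assumption and no imputation model.

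Chapter 7 says: "At the baseline, six-month, and twelve-month visits, the blood pressure will be measured by a research protocol". It then fixes the endpoint: "The outcome blood pressure will be the similarly measured (research protocol) blood pressure at the 12 month study visit". Hypotheses 1a and 1b compare baseline with month 12, and 1c uses month 12 alone. The 6-month clinic reading has a stated use in data safety monitoring (F4). In an efficacy comparison it could enter only indirectly, as the value LOCF carries forward.

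Chapter 5 lists, as a retention barrier, disappointment with the usual-care "arm leading to lack of follow-up for the 6 and 12 month visits".

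**The concern.** A participant with no month-12 reading cannot enter the t-test unless a value is supplied. The plan expects about 80 such participants (400 − 320) and leaves open how they are handled. One listed option, deletion, would drop them from an analysis called intention-to-treat. Suitable methods are also on the list; the weakness is that none is chosen, in an open-label trial where the choice could be made after results are known.

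If loss depends on blood-pressure response, and its rate or mechanism differs by arm, completers no longer represent the randomized groups. The 6-month research SBP is the best information already collected on how someone was responding before leaving, and the efficacy plan does not use it. LOCF freezes the last value, so its error depends on when people leave and how SBP moves afterwards.

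**Working it through.** **1. The plan's own figure.** Inputs from F4: difference 5, SD of change 16, two-sided alpha 0.05, power 80%, attrition 20%. n = 2(1.960 + 0.842)² × 16²/5² = 160.7 per arm, and 160/0.8 = 200 recruited per arm. With 160 completers per arm, power is 79.8% and SE = 16√(2/160) = 1.79. The plan's figures reproduce; they are calculated on completers.

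**2. When completers mislead.** Let p be the fraction missing in an arm, and D the amount by which its missing participants' mean reduction falls short of its completers'. The all-randomized effect is the completer difference − p_I·D_I + p_C·D_C (I intervention, C usual care). Equal p and equal D cancel. If only intervention dropouts do worse, at 20% loss, a completer difference of 5 becomes 5 − 0.2D: 4.0 at D = 5 and 3.0 at D = 10. The smallest significant difference is 1.96 × 1.79 = 3.51, so significance is lost at D = (5 − 3.51)/0.2, about 7.5 mm Hg.

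**3. Simulated range.** The documents give no dropout mechanism, so these are assumptions: normal SBP, baseline mean 150, equal SD at each visit, correlation 0.5, SD of change 16; mean reductions at months 6/12 of 12/15 (intervention) and 8/10 (usual care), so the true difference is 5. Loss before month 6 is random. The log-odds of later loss shift by ±0.5 (weak) or ±1 (stronger) per 16 mm Hg of SBP change; + means poor responders leave. Loss is 15% intervention / 25% usual care unless stated. LOCF carries baseline forward for early leavers.

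| Loss depends on | Completers | LOCF | Uses 6-month SBP |
|---|---|---|---|
| Nothing (random), half early | 4.97 | 5.14 | 4.98 |
| 6-month change, same in both arms, 20%/20%, all late, +1 | 4.99 | 4.78 | 4.98 |
| 6-month change, usual care only, half early, +0.5 / −0.5 | 4.50 / 5.58 | 5.60 / 4.75 | 5.05 / 5.03 |
| 6-month change, both arms, all late, +1 / −1 | 4.33 / 5.66 | 5.41 / 4.68 | 4.99 / 5.02 |
| 6-month change, usual care only, half early, +1 / −1 | 3.98 / 5.98 | 5.92 / 4.38 | 5.00 / 4.98 |
| 6-month change, usual care only, all late, +1 / −1 | 3.27 / 6.76 | 6.29 / 3.82 | 4.97 / 5.05 |
| Unseen 12-month change, usual care only, half early, +0.5 / −0.5 | 3.92 / 6.15 | 4.77 / 5.60 | 4.29 / 5.78 |
| Unseen 12-month change, usual care only, all late, +1 / −1 | 1.57 / 8.46 | 3.77 / 6.36 | 2.61 / 7.42 |

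Monte Carlo error is about 0.07. The third and fourth rows are the moderate cases: shifts of 0.50 to 0.67, or 0.28 to 0.37 of an SE. In the third to sixth rows the last column is near 5 by construction, because later loss depends only on observed data (missing at random).

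**4. Power and type I error** (200 per arm; completers versus multiple imputation by arm). Random loss: power 80% vs 81%. Moderate: 68% vs 81% (usual care only, +0.5) and 71% vs 82% (both arms, +1). Extreme (usual care only, all late, +1): 47% vs 80%. With the opposite sign in usual care only, completer power rises to about 87% (−0.5, half early) and 96% (−1, all late). Type I error in the moderate cases is 5.8% vs 4.5% and 6.3% vs 5.8%. With 1,500 trials the Monte Carlo SE is √(0.05 × 0.95/1500), about 0.6 points, so these barely separate. In the extreme case it is 17.0% vs 4.3%.

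**5. LOCF by arithmetic.** Suppose all loss is random and before month 6, with baseline carried forward (the plan does not say it would be). For a true 5: 15 × 0.80 − 10 × 0.80 = 4.0 at 20%/20%, and 15 × 0.85 − 10 × 0.75 = 5.25 at 15%/25%. For a true 0: 10 × 0.85 − 10 × 0.75 = 1.0 at 15%/25%, and 0 at 20%/20%.

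**The case against.** The best defence has several parts, and much of it stands.

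- **The documented dropout route is not the one where the fix works best.** Chapter 5 foresees missed 6- and 12-month visits, which leaves no 6-month value to use, and it does not link that loss to blood pressure. The largest shifts assume all loss after month 6. This stands, and those rows should not set the weight of the point.
- **Retention is better protected than the attrition figure suggests.** Chapter 2, section 6, and the training text in section 4.3 keep participants in follow-up if they fail training, stop self-management or exhaust the algorithm. Chapters 5 and 6 add incentives and efforts to reach people. This stands and lowers the risk.
- **LOCF is not worthless.** Where loss depended on observed response and differed by arm, completers and LOCF fell on opposite sides of 5, so comparing them would raise a flag. Where loss depended on the unseen 12-month change, LOCF was closer to 5 than the 6-month-informed estimate in all four cases. That ordering depends on the assumed trajectories, so it does not make LOCF a dependable main check; nor do these results show it to be generally unsound.
- **The list is generic.** It may also cover covariates and questionnaires, so a missing indicator is not necessarily meant for the outcome. Clinic readings appear only as a source for imputation; the plan does not say that they replace the research measurement.

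A reader might infer that the trial will lose power or understate its effect. The documents do not support this: they give no mechanism, the sign is unknown, and with the opposite sign completer power goes up.

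**Conclusion.** The point holds as a cheap improvement in specification. No method is tied to the primary test, and a useful measurement taken in both arms is left out of the efficacy analysis. With random loss there is no bias, and using the 6-month SBP gains only about one point of power. Under the moderate assumptions the shift is about a third of an SE in either direction. Larger shifts need stronger dependence confined to one arm, or loss driven by unseen values; the largest also put all loss after month 6.

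These sizes rest on assumed trajectories, correlations and log-odds. Selected scenarios rerun at correlations 0.3 and 0.7 agreed to about 0.1. They show a range, not a prediction. Two further inferences would go too far: that the sample size is wrong (it reproduces), and that the plan has committed to a completer analysis (deletion is only one listed option, although the power figure is calculated on completers).

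**What to change.** In Chapter 9, name one primary estimator that uses the 6-month research SBP:

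- (a) multiple imputation by arm from baseline and 6-month SBP, followed by the planned t-test; or
- (b) a likelihood repeated-measures model with baseline, 6- and 12-month SBP as responses and the month-12 contrast primary.

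State the missing-at-random assumption. Rule out deletion and a missing-outcome indicator for the primary outcome. Make an arm-specific delta or tipping-point analysis the main sensitivity check; it is a form of the pattern-mixture modeling already listed. Use clinic readings as auxiliary variables in the imputation, not as substitutes for the outcome.

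The cost is SAP wording and modest analysis work, with no new data, visits or participants; option (a) keeps the planned test. The downside is reliance on missing at random. The change recovers little for participants who miss both follow-up visits and helps only partly if loss depends on unseen values. The tipping-point analysis shows how far the conclusion depends on that assumption, but does not remove the bias.
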